5. SAMPLE SIZE CONSIDERATIONS

The null hypothesis corresponding to the primary analysis of this study is:

H0: The sum of the probability that a subject assigned to the 5-day arm will have a higher DOOR than if assigned to the 10-day arm plus one-half the probability of equal DOORs is 50% (i.e., no difference in DOOR).

The primary study sample size is based on a superiority test of the null hypothesis above, under an assumed alternative hypothesis that the sum of the probability that a subject assigned to the 5-day arm will have a higher DOOR than if assigned to the 10-day arm plus one-half the probability of equal DOORs is 60% (p=60%).

A sample size of 360 (180 per arm) provides 90% power using a 2-sided alpha=0.05 with a Wilcoxon Mann-Whitney U test (see calculation below). If p=65% or 70%, then a total sample size of 160 (80 per arm) or 90 (45 per arm), respectively, would be required. The sample size is inflated by ~10% based on an estimate from a similar study, in order to account for loss to follow-up resulting in a total sample size of 400 (200/arm).

Sample size calculations were based on the formula below (Noether 1987):

$$N = \frac{(z_{\alpha} + z_{\beta})^2}{12c(1-c)\left(p'' - \frac{1}{2}\right)^2}$$

$$z_{\alpha} = \Phi^{-1}(0.975); z_{\beta} = \Phi^{-1}(0.90); (90\% \text{ power for two-sided test with } 5\% \text{ Type I error})$$

$$c = 0.5 \text{ (equal allocation to treatment arms)}$$

$$p'' = 0.6 \text{ (Pr(Higher DOOR) under alternative hypothesis)}$$

Note that the primary analysis statistical methods use the ITT analysis population and will account for missing data with multiple imputation. The exact analysis method was not used for the power calculation because it would require an excessive amount of assumptions about the nature and patterns of missing data in the final dataset and relationships of components of the imputation model to the primary outcome. Instead, a complete case analysis assuming 90% evaluable for analysis was used to obtain approximately 90% power in the actual analysis.

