6.5.7. Desirability of Outcome Ranking (DOOR) at OAV#1 or OAV#2

DOOR at OAV#1 is defined by ranking all subjects (pooling together both treatment arms) according to OCR at OAV#1 (lower is better) and using the number of days of antibiotic use at OAV#1 (lower is better) as a tie-breaker for comparing the ranking of two subjects with the same OCR. DOOR at OAV#2 is defined by ranking all subjects (pooling together both treatment arms) according to OCR at OAV#2 (lower is better) and using the number of days of antibiotic use at OAV#2 (lower is better) as a tie-breaker for comparing the ranking of two subjects with the same OCR. DOOR at OAV#1 or at OAV#2 is missing only if OCR or number of days of antibiotic use is missing for the respective OAV.

The ranking algorithm for DOOR is implemented as follows. A score variable is created that adds the number of days of antibiotic use (as defined in Section 6.5.6) divided by 100 to the OCR. Subjects are then ranked (DOOR) by the score, with the highest rank going to the subject with the lowest score, and the lowest rank going to the subject with the highest score. Tied scores result in a DOOR equal to the mean of the tied ranks. The algorithm is exemplified below using a simple scenario with 4 subjects.

Suppose Subject A has an OCR of 1 and 5 days of antibiotic use in the study period (score=1.05), Subject B has an OCR of 1 and 0 days of antibiotic use (score=1.00), Subject C has an OCR of 2 and 0 days of antibiotic use (score=2.00), and Subject D has an OCR of 1 and 5 days of antibiotic use (score=1.05). Because Subject B has the lowest score, Subject B is given DOOR=1 (the highest rank). Because Subject A and Subject D tie for the next lowest score, they both receive the mean of the next 2 available ranks (2 and 3, which has mean 2.5), and so the DOOR for both Subject A and Subject D is 2.5. Finally, Subject C has the highest score and therefore receives the worst available rank, which is DOOR=4.

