8.1.1. Primary Analysis of DOOR at Outcome Assessment Visit #1

DOOR at Outcome Assessment Visit #1 is defined in Section 3.3.

The null hypothesis corresponding to the primary analysis of this study is:

H0: The sum of the probability that a subject assigned to the 5-day arm will have a higher DOOR at Outcome Assessment Visit #1 than if assigned to the 10-day arm plus one-half the probability of equal DOORs at Outcome Assessment Visit #1 is 50% (i.e., no difference in DOOR at Outcome Assessment Visit #1).

The above null hypothesis can be tested using a Mann-Whitney U Test (Evans 2015).

The primary analysis will use multiple imputation with a linear model to impute missing DOOR at Outcome Assessment Visit #1 outcomes. Details of multiple imputation methods are described in Section 8.4.1.

For each of the 20 complete multiply imputed datasets, a Mann-Whitney U statistic will be computed using randomization to short course versus randomization to standard course to define the binary grouping and DOOR at Outcome Assessment Visit #1 as the outcome. The U statistics are asymptotically normal distributed, and so they can be combined into a single test statistic using Rubin's Rules (Marshall 2009).

Defining the following:

n_1 : number of subjects in ITT cohort randomized to a short course of antibiotics

n_2 : number of subjects in ITT cohort randomized to a standard course of antibiotics

m : number of imputed datasets ($m = 20$)

Q_i : U statistic computed from the i^{th} multiply imputed dataset

$$\bar{Q} = \frac{1}{m} \sum_{i=1}^m Q_i$$

Q_0 : the expected value of a U statistic under the null hypothesis ($Q_0 = \frac{n_1 n_2}{2}$)

\bar{U} : The within imputation variance (this is not the mean of the U statistics). Correcting for ties, the formula for the within imputation variance of U is:

$$\bar{U} = \text{Var}(Q_i) = \frac{n_1 n_2}{12} \left[(n_1 + n_2 + 1) - \sum_{c=1}^D (M_c^3 - M_c) \right] \quad (\text{Lehmann 1975, Zhao 2008}),$$

where M_c is the number of tied ranks for the c^{th} value DOOR in the dataset and D is the number of distinct values of DOOR in the dataset. Because the numbers of tied ranks should be very similar across the 20 multiply imputed datasets, the number of ties will be counted from the first imputed dataset only, and those counts will be used to compute the corrected variance.

$$B = \frac{1}{m-1} \sum_{i=1}^m (Q_i - \bar{Q})^2$$

$$T = \bar{U} + \frac{m+1}{m} B$$

$$W = \frac{(\bar{Q} - Q_0)^2}{T}$$

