8.2. Secondary Efficacy Analyses

8.2.1. Analysis of DOOR at Outcome Assessment Visit #2, Performed as ITT in an Analogous Manner to the Primary Analysis

DOOR at Outcome Assessment Visit #2 is defined in Section [3.3](#).

The null hypothesis corresponding to this analysis is:

H0: The sum of the probability that a subject assigned to the 5-day arm will have a higher DOOR at Outcome Assessment Visit #2 than if assigned to the 10-day arm plus one-half the probability of equal DOORs at Outcome Assessment Visit #2 is 50% (i.e., no difference in DOOR at Outcome Assessment Visit #2).

The above null hypothesis can be tested using a Mann-Whitney U Test (Evans 2015).

This analysis will use multiple imputation with a linear model to impute missing DOOR at Outcome Assessment Visit #2 outcomes. Details of multiple imputation methods are described in Section [8.4.1](#).

For each of the 20 complete multiple imputation datasets, a Mann-Whitney U statistic will be computed using randomization to short course versus randomization to standard course to define the binary grouping and DOOR at Outcome Assessment Visit #2 as the outcome. The U statistics are asymptotically normal distributed, and so they can be combined into a single test statistic using Rubin's Rules (Marshall 2009).

Defining the following:

n_1 : number of subjects in ITT cohort randomized to a short course of antibiotics

n_2 : number of subjects in ITT cohort randomized to a standard course of antibiotics

m : number of imputed datasets ($m = 20$)

Q_i : U statistic computed from the i^{th} multiply imputed dataset

$$\bar{Q} = \frac{1}{m} \sum_{i=1}^m Q_i$$

Q_0 : the expected value of a U statistic under the null hypothesis ($Q_0 = \frac{n_1 n_2}{2}$)

\bar{U} : The within imputation variance (this is not the mean of the U statistics). Correcting for ties, the formula for the within imputation variance of the Mann-Whitney U statistic is:

$$\bar{U} = \text{Var}(Q_i) = \frac{n_1 n_2}{12} \left[(n_1 + n_2 + 1) - \sum_{c=1}^D (M_c^3 - M_c) \right] \quad (\text{Lehmann 1975, Zhao 2008}),$$

where M_c is the number of tied ranks for the c^{th} value DOOR in the dataset and D is the number of distinct values of DOOR in the dataset. Because the numbers of tied ranks should be very similar across the 20 multiply imputed datasets, the number of ties will be counted from the first imputed dataset only, and those counts will be used to compute the corrected variance.

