$$B = \frac{1}{m-1} \sum_{i=1}^m (Q_i - \bar{Q})^2$$

$$T = \bar{U} + \frac{m+1}{m} B$$

$$W = \frac{(\bar{Q} - Q_0)^2}{T}$$

$$r = \frac{m+1}{m} \frac{B}{\bar{U}}$$

$$\nu = (m - 1) \left(1 + \frac{1}{r} \right)^2$$

Under null hypothesis corresponding to the primary analysis of this study,

$$W \sim F_{1,\nu}$$

This F-distribution is used to compute a p-value (one-sided probability) from the overall test statistic W . The null hypothesis will be rejected if $p < 0.05$.

A corresponding 95% confidence interval for U will be computed using the overall test statistic W through the inversion of the F-test. Dividing the bounds of this confidence interval by $n_1 n_2$ will yield the bounds for the 95% confidence interval of $\text{Pr}(\text{Higher DOOR in short course}) + 0.5 \text{Pr}(\text{Equal DOOR in short course})$. Thus, the confidence interval is given by:

$$95\% \text{ CI: } \left(\frac{\bar{Q} - \sqrt{T \times F_{0.95,1,\nu}}}{n_1 n_2}, \frac{\bar{Q} + \sqrt{T \times F_{0.95,1,\nu}}}{n_1 n_2} \right)$$

A point estimate of the probability will be obtained by dividing \bar{Q} by $n_1 n_2$. Results will be shown in [Table 15](#).

8.2.2. Sensitivity Analyses for the DOOR at Outcome Assessment Visits #1 and #2 ITT analyses.

In addition to the ITT analysis of the DOOR at Outcome Assessment Visits #1 and #2, analyses using alternative analysis populations or imputation strategies will be performed: (1) CC analyses. (2) ATP analyses. (3) Worst case analyses. All of these analyses will test the null hypotheses described in Section 8.1.1 and Section 8.2.1 using the Mann-Whitney U Test, estimate $\Pr(\text{Higher DOOR in short course}) + 0.5 \Pr(\text{Equal DOOR})$ using U divided by the number of pairwise comparisons, and will compute confidence intervals by (1) inverting the Mann-Whitney U Test and (2) using a non-parametric bootstrap. Results will be shown in [Table 16](#) and [Table 17](#) for Outcome Assessment Visits #1 and #2, respectively.

Confidence intervals from inverting the Mann-Whitney U Test:

$$\left(\frac{U}{n_1 n_2} - 1.96 \times \sqrt{\frac{\text{Var}(U)}{(n_1 n_2)^2}}, \frac{U}{n_1 n_2} + 1.96 \times \sqrt{\frac{\text{Var}(U)}{(n_1 n_2)^2}} \right)$$

Correcting for ties, the formula for the variance of U is:

$$\text{Var}(U) = \frac{n_1 n_2}{12} \left[(n_1 + n_2 + 1) - \sum_{c=1}^D (M_c^3 - M_c) \right] \quad (\text{Lehmann 1975, Zhao 2008}),$$

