² Obtained through using inversion of the Mann-Whitney U test with a normal approximation and assuming the null hypothesis distribution variance $\text{Var}(U) = n_1 n_2 (n_1 + n_2 + 1) / 12$.

³ 2.5th and 97.5th percentiles of Pr (Higher DOOR) obtained by repeatedly re-sampling of the empirical distributions of DOOR scores by treatment arm.

⁴ P-value obtained by Mann-Whitney U Test.

Table 17: Sensitivity Analyses of DOOR at Outcome Assessment Visit #2

Analysis	Pr (Higher DOOR) ¹	Normal Approx. 95% CI ²	Bootstrapped 95% CI ³	P-value ⁴
Complete Case (CC-V2)				
According-to-Protocol (ATP-V2)				
Worst Case (ITT)				

¹ Probability of Higher DOOR in Short-Course Arm at Outcome Assessment Visit #2 + 0.5 Probability of Equal DOOR.

² Obtained through using inversion of the Mann-Whitney U test with a normal approximation and assuming the null hypothesis distribution variance $\text{Var}(U) = n_1 n_2 (n_1 + n_2 + 1) / 12$.

³ 2.5th and 97.5th percentiles of Pr(Higher DOOR) obtained by repeatedly re-sampling of the empirical distributions of DOOR scores by treatment arm.

⁴ P-value obtained by Mann-Whitney U Test.

Table 18: Risk of Mild, Moderate, or Severe Solicited Event from Day 1 to Day 5 (CC-V1 Cohort) by Treatment Group

Event	Standard Course (N=X)			Short Course (N=X)			Risk Difference		P-value ¹
	n	%	95% CI	n	%	95% CI	%	95% CI	
Any Event									
Irritability									
Vomiting									
Diarrhea									
Allergic Reaction									
Stomatitis									
Candidiasis									

Note: N=X indicates the number of subjects in the CC-V1 analysis population and the respective treatment group with complete records of solicited events recorded from Day 1 to Day 5.

¹ P-value obtained by Fisher Exact Test.

Table 19: Risk of Moderate or Severe Solicited Event from Day 1 to Day 5 (CC-V1 Cohort) by Treatment Group

Event	Standard Course (N=X)			Short Course (N=X)			Risk Difference		P-value ¹
	n	%	95% CI	n	%	95% CI	%	95% CI	
Any Event									
Irritability									
Vomiting									
Diarrhea									
Allergic Reaction									
Stomatitis									
Candidiasis									

Note: N=X indicates the number of subjects in the CC-V1 analysis population and the respective treatment group with complete records of solicited events recorded from Day 1 to Day 5.

¹ P-value obtained by Fisher Exact Test.

Table 20: Risk of Severe Solicited Event from Day 1 to Day 5 (CC-V1 Cohort) by Treatment Group

Event	Standard Course (N=X)			Short Course (N=X)			Risk Difference		P-value ¹

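### The tie-corrected variance in the primary test lacks its divisor and comes out negative, so the primary p-value and confidence interval cannot be computed as written

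*SAP*

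**What the plan says.** SAP 8.1.1 computes a Mann-Whitney U statistic in each of 20 imputed datasets and combines them by Rubin's rules. The within-imputation variance is introduced with "Correcting for ties, the formula for the within imputation variance of U is". The expression that follows is n1·n2/12 × [(n1+n2+1) − Σ(Mc³ − Mc)], where Mc is the number of children sharing the c-th DOOR value. In the SAP's notation the bracket reads "n_1 + n_2 + 1) - \sum_{c=1}^D (M_c^3 - M_c", with nothing under the sum.

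The same expression appears in 8.2.1 ("Correcting for ties, the formula for the within imputation variance of the Mann-Whitney U statistic is") and in 8.2.2 ("Correcting for ties, the formula for the variance of U is").

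Footnote 2 of Tables 16 and 17 describes the normal-approximation interval of 8.2.2 differently: "Obtained through using inversion of the Mann-Whitney U test with a normal approximation and assuming the null hypothesis distribution variance" n1·n2·(n1+n2+1)/12, which has no tie term. So the SAP holds two formulas for one interval. Neither document gives the correct tie-corrected form.

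**The concern.** The tie-corrected null variance of U is n1·n2/12 × [(n1+n2+1) − Σ(Mc³ − Mc)/((n1+n2)(n1+n2−1))]. With the divisor, ties reduce the variance modestly. Without it, the cubed group sizes swamp n1+n2+1.

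This variance is a term of T. T is the denominator of W, which gives the p-value, and T stands under the square root in the confidence interval. The variance also enters r and ν. The other analyses that inherit it are:

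- the interim test at p<0.001 (SAP 6.6, by the method of 8.1.1) and the predicted intervals (6.6.1, by 8.2.2);
- DOOR at Visit #2 (8.2.1);
- the ITT analyses of ordinal clinical response (OCR), including the 0.40 non-inferiority check (8.2.6.1 and 8.2.6.2);
- the normal-approximation intervals for the complete-case, according-to-protocol and worst-case analyses (8.2.2);
- the subgroup and site analyses (8.3.2).

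**Working it through.** **1. The plan's own figure.** The SAP states no value for the variance. Its related figure is the sample size: "A sample size of 360 (180 per arm) provides 90% power using a 2-sided alpha=0.05". Noether's formula (SAP 5) gives (1.960+1.282)²/(12×0.5×0.5×0.1²) = 10.507/0.03 = 350.2, so 351. The stated 360 gives 90.8% power, and 360/0.9 = 400. This reproduces. Noether's formula ignores ties, so the defect does not touch the sample size.

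**2. The SAP's four-subject example (6.5.7).** The ranks are 1, 2.5, 2.5 and 4, with one tied pair, so Σ(M³−M) = 8−2 = 6. The SAP assigns no arms; I assume two per arm.

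- As written: (4/12)×(5−6) = −0.33.
- With the divisor 4×3 = 12: (4/12)×(5−6/12) = 1.5.
- Direct enumeration: the six allocations give rank sums 3.5, 3.5, 5, 5, 6.5, 6.5, with mean 5 and variance (4×1.5²)/6 = 1.5.

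The divided form is exact and the printed form is impossible.

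**3. The primary analysis at planned size.** Inputs: n1 = n2 = 200 (SAP 5); 8 OCR levels (SAP Table 1); 0 to 5 antibiotic days at Visit #1 (6.5.6); score = OCR + days/100 (6.5.7). Observed scores can therefore take at most 8×6 = 48 values. The bracket starts at 200+200+1 = 401, so one group of 8 tied children (512−8 = 504) already makes it negative.

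The tie sum is smallest when children are spread as evenly as possible:

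- 360 observed and 40 imputed without ties: 24 groups of 8 and 24 of 7 give 24×504 + 24×336 = 20,160. Variance = 40,000/12 × (401−20,160) = −65.9 million.
- All 400 observed: 16 groups of 9 and 32 of 8 give 16×720 + 32×504 = 27,648. Variance = −90.8 million.

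**4. Can the between-imputation term rescue T?** T = within-imputation variance + (21/20)·B. With 20 imputed children per arm, only 200² − 180² = 7,600 pairs can change between imputations. B is largest when half of the 20 values of U lie at each end of that range: (20/19)×3,800² = 15.2 million, so 1.05·B ≤ 16.0 million. If all 40 missing children were in one arm, 40×200 = 8,000 pairs could change, B ≤ (20/19)×4,000² = 16.8 million and 1.05·B ≤ 17.7 million. Either way T is negative, W is negative, and the interval requires the square root of a negative number.

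**5. Typical size.** The documents give no expected OCR distribution. These three are assumptions, with the same OCR pattern in both arms, 0 against 5 antibiotic days, and 400 children observed:

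| OCR 1 to 8 (%) | Tie sum | Variance as written | Variance with divisor |
|---|---|---|---|
| 50/25/10/3/10/1.5/0.5/0 | 2,282,088 | −7.6 billion | 1,289,004 |
| 30/30/15/5/15/3/2/0 | 974,160 | −3.2 billion | 1,316,321 |
| 12.5 each | 249,600 | −0.83 billion | 1,331,454 |

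Without ties the variance is 40,000/12 × 401 = 1,336,667. For the first row, a permutation check with 40,000 draws gave 1,284,279, in line with the divided form. With the divisor that row gives an estimate of 0.667 and a 95% interval of 0.611 to 0.722. As written, W = −0.006 and there is no interval.

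**6. Analyses that inherit the formula, at their most favourable spread.**

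- OCR at Visit #1, 360 observed: 8 groups of 45 give 8×91,080 = 728,640, and a variance of −2.4 billion.
- DOOR at Visit #2, 360 observed: 8×19 = 152 possible scores; 56 groups of 3 and 96 of 2 give 56×24 + 96×6 = 1,920, and a variance of −5.1 million.
- Interim, 120 observed (60 per arm): 24 groups of 3 and 24 of 2 give 24×24 + 24×6 = 720, and a variance of 300×(121−720) = −179,700.

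**The case against.** **Lost in text extraction.** The divisor could have been dropped when the PDF was read. This is unlikely: the expression is identical in three places, and the neighbouring fractions, such as n1·n2/12, survived. A look at the source PDF would settle it.

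**The error shows itself.** A negative variance stops the program or returns p = 1, so it cannot quietly give a wrong significant result. The SAP cites two references for the formula, and protocol 11.4.1 asks for the same analysis without printing it. The repair leaves no analytic choice. All of this is true, and it makes a transcription slip the likely cause. It does not make the stated rule usable. Stock Mann-Whitney routines apply the right correction, but the SAP prescribes a Rubin combination built on its own variance expression, with tie counts from the first imputed dataset. Someone must code it by hand, with a conflicting no-tie formula in the table footnotes.

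**Reach.** The bootstrap intervals in 8.2.2 do not use this variance, and the p-values in Tables 16 and 17 are described only as coming from the Mann-Whitney test. At Visit #2 the most favourable variance (−5.1 million) is smaller in size than the 16.0 million cap on 1.05·B, so a negative T is not proven there without an outcome assumption. These limits stand. They do not affect the primary analysis.

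**Conclusion.** The formula is wrong as written. For the primary analysis the failure needs no assumption about outcome rates. It follows from 200 per arm, at most 48 possible scores and about 10% missing data: the within-imputation variance is at most −65.9 million, and T and W are negative. The billion-scale figures and the corrected values of 1.29 to 1.33 million rest on assumed OCR distributions. In those examples the correct variance is within 4% of the untied value (1,289,004 against 1,336,667 is 3.6% lower), so inserting the divisor restores an ordinary, well-behaved test. Because this is the pre-specified primary formula, it must be corrected. Otherwise the programmer has to choose a replacement after the plan is fixed.

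**What to change.** - In SAP 8.1.1, 8.2.1 and 8.2.2, replace the expression with Var(U) = n1·n2/12 × [(n1+n2+1) − Σ(Mc³ − Mc)/((n1+n2)(n1+n2−1))].
- In footnote 2 of Tables 16 and 17, replace the no-tie variance with the same formula, so that text and table shells describe one interval.
- The analyses that refer back to these sections then need no further change.

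The cost is SAP wording only. Design, data collection, conduct and sample size are unchanged.

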8.2. Secondary Efficacy Analyses

8.2.1. Analysis of DOOR at Outcome Assessment Visit #2, Performed as ITT in an Analogous Manner to the Primary Analysis

DOOR at Outcome Assessment Visit #2 is defined in Section [3.3](#).

The null hypothesis corresponding to this analysis is:

H0: The sum of the probability that a subject assigned to the 5-day arm will have a higher DOOR at Outcome Assessment Visit #2 than if assigned to the 10-day arm plus one-half the probability of equal DOORs at Outcome Assessment Visit #2 is 50% (i.e., no difference in DOOR at Outcome Assessment Visit #2).

The above null hypothesis can be tested using a Mann-Whitney U Test (Evans 2015).

This analysis will use multiple imputation with a linear model to impute missing DOOR at Outcome Assessment Visit #2 outcomes. Details of multiple imputation methods are described in Section [8.4.1](#).

For each of the 20 complete multiple imputation datasets, a Mann-Whitney U statistic will be computed using randomization to short course versus randomization to standard course to define the binary grouping and DOOR at Outcome Assessment Visit #2 as the outcome. The U statistics are asymptotically normal distributed, and so they can be combined into a single test statistic using Rubin's Rules (Marshall 2009).

Defining the following:

n_1 : number of subjects in ITT cohort randomized to a short course of antibiotics

n_2 : number of subjects in ITT cohort randomized to a standard course of antibiotics

m : number of imputed datasets ($m = 20$)

Q_i : U statistic computed from the i^{th} multiply imputed dataset

$$\bar{Q} = \frac{1}{m} \sum_{i=1}^m Q_i$$

Q_0 : the expected value of a U statistic under the null hypothesis ($Q_0 = \frac{n_1 n_2}{2}$)

\bar{U} : The within imputation variance (this is not the mean of the U statistics). Correcting for ties, the formula for the within imputation variance of the Mann-Whitney U statistic is:

$$\bar{U} = \text{Var}(Q_i) = \frac{n_1 n_2}{12} \left[(n_1 + n_2 + 1) - \sum_{c=1}^D (M_c^3 - M_c) \right] \quad (\text{Lehmann 1975, Zhao 2008}),$$

where M_c is the number of tied ranks for the c^{th} value DOOR in the dataset and D is the number of distinct values of DOOR in the dataset. Because the numbers of tied ranks should be very similar across the 20 multiply imputed datasets, the number of ties will be counted from the first imputed dataset only, and those counts will be used to compute the corrected variance.

$$B = \frac{1}{m-1} \sum_{i=1}^m (Q_i - \bar{Q})^2$$

$$T = \bar{U} + \frac{m+1}{m} B$$

$$W = \frac{(\bar{Q} - Q_0)^2}{T}$$

$$r = \frac{m+1}{m} \frac{B}{\bar{U}}$$

$$\nu = (m - 1) \left(1 + \frac{1}{r} \right)^2$$

Under null hypothesis corresponding to the primary analysis of this study,

$$W \sim F_{1,\nu}$$

This F-distribution is used to compute a p-value (one-sided probability) from the overall test statistic W . The null hypothesis will be rejected if $p < 0.05$.

A corresponding 95% confidence interval for U will be computed using the overall test statistic W through the inversion of the F-test. Dividing the bounds of this confidence interval by $n_1 n_2$ will yield the bounds for the 95% confidence interval of $\text{Pr}(\text{Higher DOOR in short course}) + 0.5 \text{Pr}(\text{Equal DOOR in short course})$. Thus, the confidence interval is given by:

$$95\% \text{ CI: } \left(\frac{\bar{Q} - \sqrt{T \times F_{0.95,1,\nu}}}{n_1 n_2}, \frac{\bar{Q} + \sqrt{T \times F_{0.95,1,\nu}}}{n_1 n_2} \right)$$

A point estimate of the probability will be obtained by dividing \bar{Q} by $n_1 n_2$. Results will be shown in [Table 15](#).

8.2.2. Sensitivity Analyses for the DOOR at Outcome Assessment Visits #1 and #2 ITT analyses.

In addition to the ITT analysis of the DOOR at Outcome Assessment Visits #1 and #2, analyses using alternative analysis populations or imputation strategies will be performed: (1) CC analyses. (2) ATP analyses. (3) Worst case analyses. All of these analyses will test the null hypotheses described in Section 8.1.1 and Section 8.2.1 using the Mann-Whitney U Test, estimate $\Pr(\text{Higher DOOR in short course}) + 0.5 \Pr(\text{Equal DOOR})$ using U divided by the number of pairwise comparisons, and will compute confidence intervals by (1) inverting the Mann-Whitney U Test and (2) using a non-parametric bootstrap. Results will be shown in [Table 16](#) and [Table 17](#) for Outcome Assessment Visits #1 and #2, respectively.

Confidence intervals from inverting the Mann-Whitney U Test:

$$\left(\frac{U}{n_1 n_2} - 1.96 \times \sqrt{\frac{\text{Var}(U)}{(n_1 n_2)^2}}, \frac{U}{n_1 n_2} + 1.96 \times \sqrt{\frac{\text{Var}(U)}{(n_1 n_2)^2}} \right)$$

Correcting for ties, the formula for the variance of U is:

$$\text{Var}(U) = \frac{n_1 n_2}{12} \left[(n_1 + n_2 + 1) - \sum_{c=1}^D (M_c^3 - M_c) \right] \quad (\text{Lehmann 1975, Zhao 2008}),$$

where M_c is the number of tied ranks for the c^{th} value DOOR in the dataset and D is the number of distinct values of DOOR in the dataset.

Confidence intervals using a non-parametric bootstrap:

$$\left(\frac{U_{0.025}}{n_1 n_2}, \frac{U_{0.975}}{n_1 n_2} \right)$$

Where $U_{0.025}$ and $U_{0.975}$ are chosen as the 250th and 9750th values in a sorted array of 10,000 values of Mann Whitney U statistics generated from random resampling (number of values sampled to generate the statistic will be equal to the number of subjects in the respective analysis population) of the empirical distributions of DOOR scores in each treatment arm for the given analysis population.

